6.3 Key Definitions

Baseline:

Unless stated otherwise, baseline will be defined for each subject and will be defined as the last non-missing measurement (including repeated and unscheduled assessments) before IV infusion of the study drug, NS101. Post-baseline will be considered as all measurements collected after end of IV infusion of the study drug, NS101. Unknown, Not Done, Not Applicable and other classifications of missing data will not be considered when calculating baseline observations unless the finding is a valid categorical observation.

Study day:

Study day will be calculated using study drug administration date as the reference date. If the date of interest occurs on or after the study drug administration date, study day will be calculated as follows: date of interest – study drug administration date + 1 = study day. If the date of interest occurs prior to the study drug administration date, study day will be calculated as follows: date of interest – study drug administration date = study day. There will be no study day 0.

Prior medication:

Prior medication is defined as any medication which has a start date before screening.

Concomitant medication:

Concomitant medication is defined as any medication which has a dosing date after screening and before the last study day.

Body mass index (BMI):

The BMI is a value derived from the mass (weight) and height of a person, calculated by the following equation: Weight (kg) / Height (m)² = BMI

Nominal timepoint value:

Nominal timepoint value is the value at a scheduled timepoint or the average of a set of values around a scheduled timepoint.

This document is confidential.

6.4 Drop-Outs and Missing Data

There will be no imputation for missing data, unless otherwise specified. Missing data shall be presented in subject listings as either “UN” for an unknown day, “UNK” for an unknown month, “UNKN” if year is unknown or “N/A” (not applicable), with the corresponding definition in the footnotes.

In the case of withdrawal of consent, all data from subjects who withdraw from the study will be included in all summaries up to the time of withdrawal. For all other withdrawals, all data captured will be included in the safety summaries.

For PK analysis, only observed concentration data will be used in the data analysis except for concentration values below the lower limit of quantification (BLQ). No attempt will be made to extrapolate or interpolate estimates for missing data.

6.5 Protocol Deviations

Subject data will be examined for evidence of protocol deviations. All protocol deviations will be categorized (Major, Minor, Critical or No impact) and listed by subject.

This document is confidential.

7. Subject Attributes

7.1 Subject Disposition

The number of subjects who were screened, enrolled, randomized, dosed, and completed or discontinued from the study, will be summarized. This summary table will also include the number of subjects in each analysis population. The data will be presented by cohort and overall (frequency and the percentage of subjects) and listed. If applicable, reason(s) for discontinuation will also be listed.

7.2 Inclusion and Exclusion Criteria

All recorded inclusion/exclusion criteria status will be presented in a data listing for the safety population. Each subject's inclusion or exclusion from each population will also be presented in a data listing.

7.3 Demographic and Baseline Characteristics

Demographic characteristics (including age, sex, ethnicity, race, country, and dominant hand) and baseline characteristics (body measurements of height, weight, and BMI) will be summarized by study treatment and listed by subject for the safety population. If the safety population and PK parameter population are different, then a separate table for the PK parameter population will be generated.

Descriptive statistics (n, mean, SD, min, median, and max) will be calculated for continuous variables using the last results obtained prior to study drug administration. Frequency counts and percentages will be tabulated for categorical variables.

7.4 Medical History

Medical history will be listed by subject. The latest version of the Medical Dictionary for Regulatory Activities (MedDRA, version 24.1) will be used to classify all medical history findings by system organ class (SOC) and preferred term (PT).

7.5 Medications

All prior and concomitant medications will be presented in data listings for the Randomized Population.

Concomitant medications will be coded using the latest version of the World Health Organization Drug Dictionary (WHOD). The total number of concomitant medications and the number and percentage of subjects with at least one concomitant medication will be summarized for the Safety Population. Concomitant medication data will be presented separately by anatomical therapeutic chemical (ATC) classification code (2nd level), preferred term (PT), and treatment. Note: When 2nd level classification code is not available, 1st level classification will be used instead.

7.6 Study Drug Administration

The study drug administration details including cohort, date and time of administration, frequency, route, formulation, planned dose, amount of study drug administered, and fasting status, will be listed by subject.

This document is confidential.

8. Pharmacokinetic (PK) Analyses

All serum concentration and serum PK parameter summaries, and analyses will be conducted on the PK concentration population and the PK parameter population, respectively.

Serum concentrations, collection times, and collection time deviations will be listed for the PK concentration population by dose level. The serum concentrations of NS101 will be summarized for the PK concentration population by dose level, and time point, using descriptive statistics. The individual and mean (\pm SD) concentrations for NS101 will be presented graphically on both linear and semi logarithmic scales by dose level for the PK concentration population.

8.1 Data Presentation

For all PK analyses, concentration values BLQ that occur before the first measurable concentration of the study drug will be set to “0.00”; BLQ values that occur after first measurable concentration will be set to “missing”. No imputations will be made on BLQ concentrations.

Invalid concentration values (due to bioanalytical or clinical issue) that occur prior to dosing will be replaced by “0.00”. Invalid concentration values that occur after dosing will be set to “missing” for tabulation, graphical representation, and calculation purposes.

The actual clock time for dosing start and end and the actual clock time for each collection time for the PK samples will be recorded using electronic data capture. For all sampling times, the actual sampling duration will be calculated as the difference between the sample collection actual clock time and the actual clock time of dosing end. The actual post-dose sampling times, expressed in hours and rounded off to three decimal digits, will be used to calculate the PK parameters. Pre-dose samples will always be reported as “0.000”, regardless of the time difference. Scheduled sampling times will be presented in concentration tables and mean graphs, while actual sampling times will be presented in the individual graphs in the PK section of the report. Actual sampling times also will be used for final PK parameter derivation. If actual sampling time is missing, then nominal time will be used. A listing of the actual times for PK sampling will be provided for PK samples.

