11.6 Study Treatments Administration

The study treatment will be administered in bed by IV infusion using aseptic techniques. Detailed instructions for study treatment infusion will be included in Pharmacy forms and/or Project Specific Procedure (PSP).

The body weight of each subject measured on Day -1 (check-in) will be used to calculate the exact individual dose required on a mg/kg basis, based on their assigned dose level (cohort), as presented in Table 12. The infusion will be performed over a period of approximately 60 minutes at a constant rate using a volume-controlled infusion device.

Table 12. Dose Levels per Cohort

Cohort	Dose levels of NS101*
1	1 x 0.25 mg/kg
2	1 x 0.75 mg/kg
3	1 x 1.50 mg/kg
4	1 x 3.0 mg/kg
5	1 x 6.0 mg/kg
6	1 x 12.0 mg/kg
7	1 x 24.0 mg/kg
8	1 x 48.0 mg/kg

^{*} Volume of NS101 placebo will be also determined based on subject weight and NS101 concentration.

As an example, for a human weighing 60 kg assigned to the first dose level of 0.25 mg/kg, the administered dose would be equal to 15 mg.

Approximately 1 hour prior to start of study drug infusion, an IV port will be inserted into the antecubital region and a sterile normal saline solution infusion will be initiated at fixed rate in order to keep the vein open. The study drug will be infused over approximately 60 minutes at a constant rate. At the end of the infusion, 3 mL of saline solution will be injected to flush the remaining drug into the IV catheter. The end of infusion will be set to the end of the 3 mL flush. For safety reason (e.g., administration of rescue medication), the IV line will remain opened for approximately 1 hour following completion of infusion.

The start and end times of infusion of each subject will be recorded in the source documents. Time of dosing will be set as the start of study treatment infusion.

Diluted NS101 should be used within 4 hours at room temperature. Diluted NS101 stored at 2°C to 8°C should be equilibrated to room temperature for 30 minutes prior to infusion.

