11.8.5 Time Tolerance Windows and Total Blood Volume

The time tolerance window for blood samples collected during the confinement period will be within the hour pre-dose for the pre-infusion sample, ± 3 minute for all samples collected before 8 hours post-start of infusion and ± 15 minutes for all subsequent samples collected up to 48 hours post-start of infusion. The time tolerance window for return visit samples will be ± 1 day on Days 5, 8 and 15, ± 2 days for Days 22 and 29, and ± 3 days for Day 60. The time tolerance window for CSF samples on Day 2 is ± 3 hours. Sample collections done outside the pre-defined time windows will not be considered as protocol deviations since actual post-start of infusion sampling times will be used for PK and statistical analyses. Unless otherwise specified or for subject safety, when blood draws and other procedures coincide, blood draws will have precedence. When timepoints for ECGs, vital signs, and blood draws coincide, procedures will be carried out in the said order. A dead-volume intravenous catheter will be used for blood collection to avoid multiple skin punctures, when appropriate. Otherwise, blood samples will be collected by direct venipuncture.

The planned volume of blood to be collected during the study, including that collected for eligibility and safety purposes, should not exceed 250 mL. Additional tests or blood draws could be performed, if deemed required by the Investigator or study staff.

Serum and CSF samples will be collected and processed as per the Analytical Methodology Information Sheet / Laboratory Manual.

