8.2 Serum PK Sampling Schedule

A total of 21 blood samples will be collected in each cohort for serum PK analysis: pre-start of infusion and 0.25, 0.5, 0.75, 1, 1.25, 1.5, 2, 4, 6, 8, 12, 24, 36, 48, 96, 168, 336, 504, 672, and 1416 hours post-start of infusion.

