8.4 CSF PK Sampling Schedule

Subjects included in Cohorts 5 through 8 will have one CSF sample collected, via lumbar puncture, at one of the following timepoints: 24, 36, 168, or 336 hours post-start of infusion.

NS101 concentrations in CSF will be presented in the listings, as well as the ratio of NS101 in serum to NS101 in CSF at the applicable time-matched timepoint, i.e. serum NS101/CSF NS101 at time xx hrs.

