9.1 Data Presentation

The actual clock time for dosing start and end and the actual clock time for each collection time for the PD samples will be recorded using electronic data capture. For all sampling times, the actual sampling times will be calculated as the difference between the sample collection actual clock time and the actual clock time of dosing end. The actual post-dose sampling times, expressed in hours and rounded off to three decimal digits, will be used to calculate the PD parameters. Pre-dose samples will always be reported as “0.000”, regardless of the time difference.

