9.2 Plasma PD Sampling Schedule

A total of 14 blood samples will be collected in each cohort for PD analysis: pre-dose (baseline) and 1, 4, 6, 12, 24, 36, 48, 96, 168, 336, 504, 672, and 1416 hours post-start of infusion.

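### The SAP counts actual PK and PD sampling times from the end of infusion, although the protocol and the SAP's own schedules count from the start, so Tmax and TEmax come out about 1 h too early

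*SAP*

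**What the plan says.** SAP 8.1 records clock times for both the start and the end of dosing. It then defines a sampling duration as "calculated as the difference between the sample collection actual clock time and the actual clock time of dosing end". The same paragraph continues: "The actual post-dose sampling times, expressed in hours and rounded off to three decimal digits, will be used to calculate the PK parameters". It defines no other actual time. SAP 9.1 uses the same origin for PD and leaves no doubt about the label: "the actual sampling times will be calculated as the difference between the sample collection actual clock time and the actual clock time of dosing end". In both sections the pre-dose sample is always reported at 0.000. SAP 8.1 adds that a missing actual PK time is replaced by the nominal time.

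The protocol uses the other origin. Section 11.6: "Time of dosing will be set as the start of study treatment infusion". Section 11.8.5: "actual post-start of infusion sampling times will be used for PK and statistical analyses".

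The SAP's own schedules agree with the protocol. SAP 8.2 places the serum samples at "0.25, 0.5, 0.75, 1, 1.25, 1.5, 2, 4, 6, 8, 12, 24, 36, 48, 96, 168, 336, 504, 672, and 1416 hours post-start of infusion", SAP 9.2 places the plasma PD samples at "pre-dose (baseline) and 1, 4, 6, 12, 24, 36, 48, 96, 168, 336, 504, 672, and 1416 hours post-start of infusion", and SAP 8.4 takes the CSF sample "at one of the following timepoints: 24, 36, 168, or 336 hours post-start of infusion". SAP 9.4 and 10.1 also count from the start of infusion. SAP 12 reports no change from the protocol's analysis.

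**The concern.** The two documents cannot both be followed. The SAP is the document a programmer works from, and its only formula for actual time gives the wrong origin. Because its schedules use the other origin and it declares no change, this looks like a drafting slip rather than an intended departure.

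The consequences are:

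- **Tmax and TEmax.** Both are early by the subject's infusion length. For a peak near the end of infusion, the error in Tmax is about as large as Tmax itself.
- **Time order.** Samples drawn during the infusion get negative times, while pre-dose sits at zero. The SAP has no rule for negative or tied times, so two programmers could report different Tmax and Cmax from the same data.
- **Mixed clocks.** The nominal fallback for a missing time is on the start clock. PK tables and mean graphs use scheduled post-start times, but individual graphs use actual times.
- **AUC0-24.** The interval would cover about 1 to 25 h after the start of infusion.
- **Collection time deviations.** SAP section 8 lists them. If they were taken from end-based times against the post-start schedule, each would be offset by about -60 min, against windows of 3 to 15 min up to 48 h (protocol 11.8.5).

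**Working it through.** **Inputs**

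- Post-start sampling times: 20 PK (SAP 8.2) and 13 PD (SAP 9.2).
- Infusion length T: about 60 min, with the end of infusion set at the end of the 3 mL flush (protocol 11.6). I also take T = 1.05 h, assuming a 3-minute flush, which the documents do not state.
- Contingency only: a slowed infusion may last up to 3 h (protocol 11.10).

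**Step 1: the shift**

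Time from end = time from start - T.

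| T | PK samples negative | PK tied at 0 | PD samples negative | PD tied at 0 |
|---|---|---|---|---|
| 1.00 h | 3 (0.25, 0.5, 0.75 h become -0.75, -0.50, -0.25 h) | 1 (the 1 h sample) | 0 | 1 (the 1 h sample) |
| 1.05 h | 4 | 0 | 1 | 0 |
| 3.00 h | 7 | 0 | 1 | 0 |

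**Step 2: Tmax**

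- T = 1.00 h, peak in the 1 h sample: 1.0 - 1.0 = 0.0 h if the tied sample is kept. If it is dropped, the next sample becomes the peak: 1.25 - 1.0 = 0.25 h.
- T = 1.05 h, constant rate to the end of the flush: the highest sample is at 1.25 h and is reported at 1.25 - 1.05 = 0.20 h, with Cmax unchanged.
- T = 3.00 h: the highest sample is at 4.0 h and is reported at 4.0 - 3.0 = 1.0 h.

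**Step 3: Cmax and AUC (illustrative model)**

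The documents give no human profile. I assume one compartment and a constant-rate infusion, with k = ln 2 / half-life. Half-lives are 53.7, 78, 181, 249.6 and 329.9 h (animal values in protocol 5.2.3.1 and 5.2.4.1 to 5.2.4.3), plus 24 h as an assumed lower bound. AUC is linear-up/log-down as in SAP 8.3. Negative times lie before time zero and do not enter AUC. Two treatments of time zero are possible:

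- **A:** keep the pre-dose zero and drop all non-positive post-start samples.
- **B:** place the end-of-infusion concentration at time zero (at 60 min, this is the tied 1 h sample).

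Under A at 60 min, Cmax falls by 1 - exp(-0.25k). With a 24 h half-life, k = 0.02888 and the loss is 0.72%. With 329.9 h, k = 0.00210 and the loss is 0.05%.

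Change relative to the start clock, from a half-life of 24 h to one of 329.9 h:

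| T | Measure | A | B |
|---|---|---|---|
| 1.00 h | AUC0-24 | -0.69% to +1.42% | +0.03% to +1.97% |
| 1.00 h | AUC0-t | -1.79% to -0.14% | -1.43% to -0.11% |
| 1.05 h | AUC0-24 | -0.52% to +1.65% | +0.06% to +2.09% |
| 3.00 h | AUC0-24 | -1.62% to +4.70% | +1.30% to +6.98% |

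AUC0-inf at 60 min changes by -0.1% to -1.8%, like AUC0-t.

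**Step 4: what does not change**

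Subtracting a constant from every time leaves the slope of ln concentration on time unchanged, so Kel and half-life stay the same. A shift common to all subjects leaves the ranks, and so the Kruskal-Wallis test for Tmax (SAP 8.6), unchanged. Unequal infusion lengths or mixed clocks would no longer be a common shift.

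**The case against.** **The PK wording is open to another reading.** SAP 8.1 attaches the end of dosing to a sampling duration and then uses post-dose times for the parameters. With dosing time set at the start in protocol 11.6, post-dose could be read as post-start. That reading overrides the only formula 8.1 gives, and it cannot rescue 9.1, which calls the end-based quantity the actual sampling time.

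**TEmax hardly suffers.** In the rat data of protocol 5.2.1.2, blood FAM19A5 peaks at roughly 24 to 48 h, where 1 h is about 2% to 4% (1/48 to 1/24) and well inside the 12 h spacing of the PD samples. This stands if the human peak is similar. TEmax is exploratory, and the weight of the point falls on Tmax.

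**The model is too simple.** Protocol 5.2.4.3 describes a biphasic decline in rats. With an assumed fast phase (50% to 60% of the profile, half-life 4 to 10 h) and a 180 h slow phase, dropping the 1 h sample lowers Cmax by up to about 2.5%, and AUC0-24 falls by up to about 1.8%. This widens the illustrative ranges a little. The sample counts and the Tmax shift do not depend on it. The unchanged Cmax at 63 min likewise assumes constant delivery through the flush.

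**Some consequences are soft.** CSF and antibody results are listed or summarised by nominal time or visit, so the rule barely touches them. Protocol 11.8.5 does not count out-of-window samples as deviations. The 3 h case is a contingency. All of this stands.

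**SAP 6.3 also refers to the end of infusion.** It does so in its general definition of post-baseline. That is a separate definition and does not feed the calculation of sampling times.

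**Conclusion.** The concern holds. SAP 8.1 and 9.1 state a time origin that contradicts protocol 11.6 and 11.8.5 and the SAP's own schedules, and it gives a wrong Tmax for a named secondary endpoint. The error equals the subject's infusion length, about 1 h as planned. This follows from subtraction alone and needs no model.

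The Cmax and AUC effects are small and rest on assumed profiles. The sign of the AUC0-24 change depends on half-life and on how non-positive times are handled. No primary endpoint is affected, and no test or dose-proportionality conclusion is shown to change. The offset can be reversed because start times are recorded. It should be fixed before the analysis, but it does not threaten the trial's main conclusions.

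**What to change.** In SAP 8.1 and 9.1, subtract the actual clock time of the start of dosing (start of infusion) instead of its end, for every actual-time derivation. A peak at the end of a 60-minute infusion then gives Tmax = 1.0 h, actual times line up with the nominal schedules, no post-dose sample has a negative time, and the nominal fallback is on the same clock.

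The cost is two wording edits. Both sections already record the start time, so no new data are needed.

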8.2 Serum PK Sampling Schedule

A total of 21 blood samples will be collected in each cohort for serum PK analysis: pre-start of infusion and 0.25, 0.5, 0.75, 1, 1.25, 1.5, 2, 4, 6, 8, 12, 24, 36, 48, 96, 168, 336, 504, 672, and 1416 hours post-start of infusion.

8.3 Serum PK Parameters

Serum PK parameters will be presented in data listings and summarized in tables by dose level, using descriptive statistics (n, arithmetic mean, SD, CV%, geometric mean, min, median, and max).

The serum concentrations of NS101 will be used to calculate the following parameters by standard non-compartmental methods:

Parameter	Definition
AUC _{0-inf}	area under the concentration-time curve from time zero to infinity (extrapolated), calculated as $AUC_{0-t} + C_t/\lambda_z$, where: C_t = the last measurable concentration

This document is confidential.

Parameter	Definition
AUC _{0-t}	area under the concentration-time curve from time zero until the last observed concentration
AUC ₀₋₂₄	area under the concentration-time curve from time zero to time 24 hours
Cl	apparent body clearance, calculated as dose / AUC _{0-inf}
C _{max}	maximum observed concentration
K _{el}	elimination rate constant
T _{½ el}	terminal elimination half-life, calculated as ln 2 / K _{el}
T _{max}	time when the maximum concentration is observed
Residual area	percentage of the area extrapolated for calculation of area under the concentration-time curve from time zero to infinity, calculated as [(AUC _{0-inf} - AUC _{0-t}) / AUC _{0-inf}] * 100
V _z	apparent volume of distribution, calculated as dose / (K _{el} * AUC _{0-inf})

AUC_{0-t}, AUC₀₋₂₄, and AUC_{0-inf} will be calculated using the linear trapezoidal method (linear up log down).

K_{el} is the elimination rate constant. This parameter will be the negative of the estimated slope of the linear regression of the ln-transformed serum concentration versus time profile in the terminal elimination phase. The Best-fit method, in Phoenix WinNonlin, will be used to calculate the K_{el} from at least 3 concentration data points excluding the C_{max}. Rsq adjusted, the goodness of fit statistic for the terminal elimination phase, adjusted for the number of points used in the estimation of K_{el} must be ≥ 0.8 . If the K_{el} cannot be measured (e.g.: fewer than 3 non-zero concentrations in the terminal elimination phase or Rsq adjusted < 0.8), the PK parameters derived from K_{el} (λ_z , T_{½ el}, AUC_{0-inf}, Residual area, Cl and V_z) will be presented in the Listing(s) but excluded from descriptive statistics. The timepoint where ln-linear K_{el} calculation begins (K_{el Lower}) and the actual sampling time of the last measurable concentration used to estimate the K_{el} (K_{el Upper}), as well as the Rsq adjusted for the ln-linear regression for the calculation of the elimination rate constant will be reported.

If the Residual area is $> 20\%$, the individual result will be flagged in the Listings as well as values for T_{½ el}, AUC_{0-inf}, Cl, and V_z.

